7.7.2. Medications that Promote Weight Loss

Prescription or OTC medications that promote weight loss are exclusionary if used within the 3 months prior to Visit 1 (study entry), or between study entry and randomization at Visit 3 (see Section 6.2). These medications are also not allowed at any time during the Treatment Period. If started after randomization, these medications should be immediately withdrawn. In addition, patients should not receive an intensive diet/exercise program with the intent of reducing body weight at any time during the study, other than the lifestyle and dietary measures for diabetes treatment (see Section 6.3).

Patients who use any medication from these groups during the Treatment Period will not be included in the PP Population analysis if the duration of use is >14 days (cumulative).

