5.2. Determination of Sample Size

Assuming a screen failure rate of 40%, approximately 3000 patients will need to be screened to attain approximately 1800 patients randomized to the 3 treatment groups (600 patients/group) in a 1:1:1 ratio for dulaglutide 4.5 mg, 3.0 mg, and 1.5 mg. Assuming 15% dropout rate, this will result in approximately 510 patients per arm completing 36 weeks of treatment (the primary endpoint).

The aforementioned sample size provides $\geq 80\%$ power to demonstrate superiority of at least 1 of the investigational dulaglutide doses (4.5 mg or 3.0 mg) to dulaglutide 1.5 mg with respect to the primary endpoint (change from baseline in HbA1c) at Week 36 (Visit 9). This sample size is calculated based on the assumption that there is a treatment difference (for either investigational dose) in HbA1c change from baseline of approximately -0.22%, a standard deviation (SD) of 1.1%, and a 2-sided alpha of 0.05.

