6.1.4. Multiple Comparisons/Multiplicity

To control overall Type 1 error, the graphical approach (Bretz et al. 2011) presented in [Figure GBGL.2](#) will be used to compare the treatment effect among the pre-defined parameters of interest to address the primary and the key secondary efficacy objectives defined in the protocol at Week 36 (Visit 9) for the ITT Population. In this figure, the overall significance level of 2-sided $\alpha=0.05$ will be equally split between H_1 and H_2 with 0.025 to H_1 and 0.025 to H_2 . H_5 to H_8 will only be tested if H_1 to H_4 pass. The number attached for certain edges denotes the proportion of the allocated fraction of α from a prespecified hypothesis (node), if it is confirmed, that will be passed to the next hypothesis.

This graphical approach will be conducted separately for each of the 2 estimands, and each will be tested at the full significance level of 0.05:

- Treatment-regimen estimand
- Efficacy estimand

The below graphical scheme may be revised per the observed correlation matrix using blinded data among the parameters of interest at Week 36 (Visit 9) prior to the primary DBL.

Abbreviations: D1.5 = once weekly dulaglutide 1.5 mg; D3.0 = once weekly dulaglutide 3.0 mg; D4.5 = once weekly dulaglutide 4.5 mg; FSG = fasting serum glucose; H = hypothesis; HbA1c = glycated hemoglobin A1c.

Figure GBGL.2. Graphical testing scheme for Study H9X-MC-GBGL.

- H₁*: Superiority test of dulaglutide 4.5 mg versus dulaglutide 1.5 mg in mean change from baseline in HbA1c at 36 weeks
- H₂*: Superiority test of dulaglutide 3.0 mg versus dulaglutide 1.5 mg in mean change from baseline in HbA1c at 36 weeks
- H₃*: Superiority test of dulaglutide 4.5 mg versus dulaglutide 1.5 mg in mean change from baseline in body weight at 36 weeks
- H₄*: Superiority test of dulaglutide 3.0 mg versus dulaglutide 1.5 mg in mean change from baseline in body weight at 36 weeks
- H₅*: Superiority test of dulaglutide 4.5 mg versus dulaglutide 1.5 mg in proportion of patients achieving an HbA1c <7.0% at 36 weeks

H_6 : Superiority test of dulaglutide 3.0 mg versus dulaglutide 1.5 mg in proportion of patients achieving an HbA1c <7.0% at 36 weeks

H_7 : Superiority test of dulaglutide 4.5 mg versus dulaglutide 1.5 mg in mean change from baseline in FSG at 36 weeks

H_8 : Superiority test of dulaglutide 3.0 mg versus dulaglutide 1.5 mg in mean change from baseline in FSG at 36 weeks

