6.2. Patient Populations

Six patient populations are defined for the analyses in this study with detailed information listed in [Table GBGL.2](#). Unless otherwise specified, listings will include All Randomized Patients. Efficacy analyses will be conducted for the ITT Population, and safety analyses will be conducted for the Safety Population. The primary efficacy measure (change from baseline in HbA1c) will also be evaluated in the PP and Completers populations.

In all efficacy analyses, except for treatment-regimen estimands, all data after rescue and/or treatment discontinuation (Section 6.1) will be censored. Analyses of safety parameters will be conducted for the Safety Population including the postrescue therapy data unless otherwise specified.

Table GBGL.2. Populations for Analyses

Population	Description
Entered	All patients who sign informed consent
All Randomized	All patients who are randomized
Intent to Treat (ITT)	All patients who are randomized and take at least 1 dose of study medication for an assigned treatment arm ^a
Safety	All patients who are randomized and take at least 1 dose of study medication for the assigned treatment arm
Completers	All ITT patients who have an HbA1c measure at Week 36 (Visit 9), regardless of compliance with the protocol, rescue medication, or treatment discontinuation. However, data collected after rescue and/or treatment discontinuation will be excluded
Per Protocol (PP)	All ITT patients who meet all of the following criteria: 
 • Have no important protocol deviation that could impact the assessment of the primary endpoint (Section 6.8) • At least 75% compliant with study drug administration through Week 36 (Visit 9) • Complete the treatment period through 36 weeks (Visit 9) • Have a value of the primary efficacy measure (HbA1c) at Week 36 (Visit 9) excluding data collected after treatment discontinuation or initiation of new antihyperglycemic therapy

Abbreviation: HbA1c = glycated hemoglobin.

a Analyses using the treatment-regimen estimand will include all patients in the ITT population who have a baseline measurement for the parameter of interest, while analyses using the efficacy estimand will include patients in the ITT population who have a baseline and at least 1 postdose measurement for the parameter of interest.

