6.8. Important Protocol Deviations

Important protocol deviations will be summarized descriptively by treatment and listed for all randomized patients. All important deviations related to study inclusion or exclusion criteria, conduct of the trial, patient management, or patient assessment will be described. The rationale for choosing certain important protocol deviations as exclusionary from the PP Population will be based on their potential effect on the primary efficacy measure. The following protocol conditions as well as other conditions identified at the site and agreed upon by the study team may result in exclusion from the PP Population along with the criteria listed in [Table GBGL.2](#):

- informed consent was never obtained
- patients who are randomized but the informed consent date is missing
- patients who have an HbA1c $<7.5\%$ or $>11.0\%$ at study entry (Visit 1)
- patients who have known type 1 diabetes
- patients who had any hematologic condition that may have interfered with HbA1c measurement (for example, hemolytic anemias, sickle-cell disease)
- excluded medication:
 - weight loss agents if the duration of use is 14 days (cumulative) during the treatment period
 - any new glucose-lowering medication initiated after randomization at Visit 3 and prior to Visit 11 (end of treatment period) for >14 days, except for study drug, rescue therapy, glucose-lowering medications initiated after study drug discontinuation, or short-term use of insulin (≤ 14 days) for management of medical emergencies
 - >14 consecutive days' use of systemic glucocorticoid during the treatment period

- patients who have a missing HbA1c at baseline (both Visit 1 and Visit 3) or at 36 weeks (Visit 9)
- patients who do not have an overall compliance with study drug of at least 75% up to 36 weeks

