Appendix 1.

Summary of the Data and Primary Analysis for the Primary and Secondary Efficacy Endpoints by Type of Estimand

	Efficacy Estimand	Treatment-Regimen Estimand
Data		
Data Included in the Analyses	
 All patients in the ITT population with a baseline value and at least 1 postbaseline value for the measure of interest are included. Values are excluded after treatment discontinuation or start of antihyperglycemic medications lasting >14 days. 	
 All patients in the ITT population with a baseline value for the measure of interest are included.
Primary Analysis for Each Endpoint		
Primary Endpoint: Change from baseline in HbA1c at Week 36	
 MMRM with effects for treatment, pooled country, visit, treatment-by-visit interaction, and baseline HbA1c as a covariate, 	
 If the Week 36 value is missing, multiple imputation will be used to impute a value such that the reference group includes patients from the same treatment group and same treatment discontinuation status (yes, no) who had a value at Week 36. ANCOVA with effects for treatment, pooled country, and baseline HbA1c as a covariate.
Secondary Endpoint: Change from baseline in body weight at Week 36	
 MMRM with effects for treatment, pooled country, baseline HbA1c stratum (<8.5%, ≥8.5%), visit, treatment-by-visit interaction, and baseline body weight as a covariate. 	
 If the Week 36 value is missing, multiple imputation will be used to impute a value such that the reference group includes patients from the same treatment group and same treatment discontinuation status (yes, no) who had a value at Week 36. ANCOVA with effects for treatment, pooled country, baseline HbA1c stratum (<8.5%, ≥8.5%), and baseline body weight as a covariate.

Summary of the Data and Primary Analysis for the Primary and Secondary Efficacy Endpoints by Type of Estimand

	Efficacy Estimand	Treatment-Regimen Estimand
Primary Analysis for Each Endpoint		

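### For body weight, the efficacy estimand keeps values recorded after sustained use of a prohibited weight-loss drug, unless the patient also stops study drug or starts a lasting antihyperglycemic medication

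*SAP*

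**What the plan says.** **Efficacy estimand.** SAP Appendix 1 gives a single data rule for HbA1c, body weight, FSG and the HbA1c target: "Values are excluded after treatment discontinuation or start of antihyperglycemic medications lasting" more than 14 days. SAP 6.1 names the same two events. SAP 6.2 extends the censoring to all efficacy analyses except those for the treatment-regimen estimand.

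**Weight-loss drugs.** Protocol Table GBGL.3 lists them among the medications that may interfere with efficacy and safety assessments. Protocol 7.7.2 bars them throughout the Treatment Period and requires withdrawal if one is started. It then states one analysis consequence: "Patients who use any medication from these groups during the Treatment Period will not be included in the PP Population analysis", provided cumulative use exceeds 14 days.

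**Per Protocol use.** SAP 6.2 says: "The primary efficacy measure (change from baseline in HbA1c) will also be evaluated in the PP and Completers populations". Protocol 10.3.3.1.1 and SAP 6.9.1.2 likewise use this population only for the primary outcome. Apart from that it appears in baseline summaries (Protocol 10.3.2.2, SAP 6.4).

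**SAP 6.8.** The matching Per Protocol criterion reads "weight loss agents if the duration of use is 14 days (cumulative) during the treatment period". It has no greater-than sign, and it sits under a lead-in that makes exclusion possible rather than certain.

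**The concern.** The protocol synopsis describes the efficacy estimand as the benefit of treatment taken according to instructions. A weight measured after several weeks on a barred weight-loss drug does not fit that description well, yet it enters the analysis. HbA1c is shielded from added glucose-lowering drugs. Body weight has no matching shield from added weight-lowering drugs.

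Body weight is not a minor endpoint here. It supplies H3 and H4 in the graphical procedure, and SAP 6.1.4 allows H5 to H8 to be tested only if H1 to H4 all pass. A distorted weight difference could therefore affect the weight claims themselves and, in the efficacy-estimand graph, access to the HbA1c-target and FSG tests. The 5% and 10% weight-loss targets and the two weight composites are under the same rule.

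**Working it through.** **Step 1. Follow a patient who takes a weight-loss drug for more than 14 days, stays on study drug and starts no antihyperglycemic medication.**

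| Rule | Applies to this patient? | Acts on body weight? |
|---|---|---|
| Cut-off at treatment discontinuation (SAP 6.1, 6.2, Appendix 1) | No | Yes |
| Cut-off at new antihyperglycemic medication lasting more than 14 days (same places) | No, as written | Yes |
| Per Protocol exclusion (Protocol 7.7.2; SAP 6.8) | Yes under the protocol, optional under the SAP | No, HbA1c only |
| Case-by-case exclusion before lock (SAP 6.1) | Possible, no criterion given | Possible |
| Tabulation of use by arm (SAP 6.5) | Yes | Descriptive only |

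No prespecified rule removes this patient's later weights from H3 or H4.

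**Step 2. The plan's own figures.** They concern HbA1c only and are not disputed. SAP 5.2 plans "approximately 1800 patients randomized to the 3 treatment groups (600 patients/group) in a" 1:1:1 ratio with 15% dropout: 600 x 0.85 = 510 per arm. It claims at least 80% "power to demonstrate superiority of at least 1 of the investigational dulaglutide doses (4.5 mg or 3.0 mg) to dulaglutide 1.5 mg", assuming a difference "in HbA1c change from baseline of approximately -0.22%, a standard deviation (SD) of 1.1%, and a 2-sided alpha of 0.05".

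- Standard error = 1.1 x sqrt(2/510) = 0.0689, and 0.22/0.0689 = 3.194.
- Power at two-sided 0.05: Phi(3.194 - 1.960) = 89.1%.
- Power at 0.025 per dose: Phi(3.194 - 2.241) = 83.0%.
- At least one dose, both with a true difference of -0.22% (simulation with a shared control arm): 93.1%.

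The claim is reproduced. For body weight the documents give no SD and no power. They give only an additional loss above 1 kg at Week 18 in Phase 2 (Protocol 5.5).

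**Step 3. Size of the bias.** If the drug adds a fixed loss in either arm, the bias in the mean difference is

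(difference between arms in the share of users whose weights are kept) x (extra loss from the drug).

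All inputs here are assumed: shares differing by 1 to 5 percentage points and an extra loss of 2 to 5 kg.

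- Low end: 0.01 x 2 kg = 0.02 kg.
- Middle: 0.02 x 5 kg, or 0.05 x 2 kg = 0.10 kg.
- High end: 0.05 x 5 kg = 0.25 kg.
- Equal use in both arms: no bias in the difference.

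With 510 patients per arm, 1 point is about 5 patients and 5 points about 26.

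**Step 4. What that would do to a weight test.** Further assumptions: weight SD of 4 to 6 kg, a true difference of 1 kg for power and of zero for error, 510 per arm, and two-sided 0.025. The text of SAP 6.1.4 gives 0.025 to each HbA1c test but does not state the levels passed on to H3 and H4. With SE = SD x sqrt(2/510):

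- More use on 1.5 mg: power = Phi((1 - bias)/SE - 2.241).
- More use on a higher dose: one-sided error = 1 - Phi(2.241 - bias/SE), against a nominal 1.25%.

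| SD | Power, no bias | Power at 0.02 / 0.10 / 0.25 kg | One-sided error at 0.02 / 0.10 / 0.25 kg |
|---|---|---|---|
| 4 kg | 96.0% | 95.3 / 91.2 / 77.4% | 1.5 / 3.3 / 10.7% |
| 5 kg | 83.0% | 81.3 / 73.7 / 56.1% | 1.5 / 2.7 / 7.5% |
| 6 kg | 66.3% | 64.3 / 56.1 / 40.3% | 1.4 / 2.4 / 5.8% |

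The right-hand figure in each set needs a 5-point imbalance and the full 5 kg still present at Week 36. That is hard to square with drugs that must be withdrawn once started.

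**The case against.** The strongest reply is that the plan does what it says. Protocol 10.3.1 and SAP 6.1 give the estimand's aim as avoiding confounding by other antihyperglycemic agents, not by every drug. Rescue and post-discontinuation therapy are expected and provided for, so they need an estimand rule. Weight-loss drugs are excluded at entry and barred afterwards, so their use is a protocol deviation. This stands as a reason to expect few cases. It does not settle how those few should be handled under an estimand also described as benefit when treatment follows instructions.

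A reader might infer three stronger things that the documents do not support:

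- *That the weight-loss rule guards the wrong endpoint.* SAP 6.8 says its Per Protocol exclusions are chosen for their possible effect on the primary efficacy measure, which is HbA1c. The rule does its stated job. What is missing is a separate rule for weight.
- *That all later weights are kept.* They drop out if the patient also stops study drug or starts a lasting antihyperglycemic medication. One listed product, liraglutide 3.0 mg, is a GLP-1 receptor agonist and could arguably trigger the second event, although the SAP does not say so. The other listed products would not obviously do so.
- *That the gap hides a benefit of the higher doses.* Nothing in the documents shows which arm would use these drugs more. The bias can run in either direction.

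The pre-lock clause in SAP 6.1 lets the study team exclude observations with a documented rationale. It names no criterion and does not mention these drugs, so it is a fallback and not a rule. Tabulation by arm would reveal an imbalance but not correct for it.

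**Conclusion.** The gap is real and minor. As written, weights recorded after sustained use of a prohibited weight-loss drug stay in the efficacy estimand for H3 and H4 unless one of the two named events also occurs, and no prespecified body-weight analysis sets them aside. Under the assumed ranges the bias is 0.02 to 0.25 kg. The low end is more plausible, because the drugs are prohibited, are to be withdrawn if started, and the trial is double-blind. More use on 1.5 mg would pull the difference toward zero; more use on a higher dose would favour that dose. The calculation rests on assumed usage, drug effect and SD. It shows scale and is not a prediction.

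The mismatch between SAP 6.8 and Protocol 7.7.2 is a separate, smaller point. The protocol sets a threshold above 14 days and a definite exclusion. The SAP names 14 days and a possible exclusion. Neighbouring items in SAP 6.8 keep the greater-than sign, so a dropped symbol is likely. If the approved SAP does carry it, only the difference between definite and possible exclusion remains. This affects the Per Protocol HbA1c analysis, not H3 or H4.

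**What to change.** 1. In SAP 6.1, 6.9.2.1.1 and Appendix 1, for the efficacy estimand of body weight, add a third cut-off: exclude values after the start of a weight-loss drug used for more than 14 days cumulatively. This relies on the same missing-at-random assumption as the existing cut-offs. State whether liraglutide 3.0 mg counts under this rule, the antihyperglycemic rule, or both.
2. Apply the same cut-off to the 5% and 10% weight-loss targets and the two weight composites. Note that wherever LOCF is used (SAP 6.1.2.2, 6.9.3), the last weight before the drug will be carried forward.
3. Leave the treatment-regimen estimand unchanged. Keeping these values is consistent with its purpose.
4. Reconcile SAP 6.8 with Protocol 7.7.2 on both the threshold and whether exclusion is mandatory.

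The cost is SAP wording and the loss of a few values. No new data are needed: Protocol 7.7 already requires drug names and dates on the eCRF, and SAP 6.5 already summarises use by arm.
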